4.11 Data Collection Forms

Study investigators, subjects, and outcome assessors will be blinded to the random assignment of treatment

Several procedures are in place to ensure data integrity and protocol compliance. We will use HIPAA-compliant electronic research data capture to support direct data entry by patients and study personnel. Web-based surveys will be based on a study-specific data dictionary defined by members of the research team with planning assistance from Pthera LLC. A research associate (RA) will oversee the automated export of study data from the web-based surveys to a relational study database in structured query language (SQL), allowing for systematic data query and verification.

Participants will complete the physical self-report measures, which will then be transcribed into the data collection form by the person responsible for data entry on the research team. For doctor-administered measures, all doctors will enter responses directly into the database.

To minimize missing data from the self-report forms, we will program unanswered question warnings into the FCRe that will alert participants in real time if they inadvertently skip a question. Then, participants can go back and answer the missed questions or, if they intentionally skipped questions, they can ignore the warning message and continue answering the remaining questions. We will also program real-time range checks in FCRe that generate error messages if a value outside the acceptable range is entered for a given field. To ensure confidentiality, data will be identified in the database only by subject number, visit number, and visit date. By recording study data in this manner, the information can be considered "de-identified" and, therefore, complies with the Health Insurance Portability and Accountability Act of 1996 (HIPAA) Privacy Standards for Individually Identifiable Health Information ("Privacy Rule"). Any information transmitted electronically will be fully encrypted and password protected. Subjects' names will not be entered into the database; each will be identified only by an identification number. Consent forms, any printed PHI, and any study measures completed on paper will be stored and filed in locked office cabinets.

4.12 Data Management

The study biostatisticians will oversee the management of the study database. The principal investigators, [name] (PI) is ultimately responsible for the quality of data collection and the overall conduct of the study, and directly supervises the study coordinators and data management staff. Data management will include doctor- and patient-rated assessments (see assessments), screening data, fidelity data, visit compliance data, and rater reliability data and safety reports. Weekly database reports will monitor enrollment, completion, attrition, dropout, and individual subject progress, as well as completion of critical assessments. Additional reports will be done as needed to monitor baseline characteristics, protocol adherence, and other issues of interest.

Transcranial Near Infrared Laser Therapy in Subjects with Major Depressive Disorder: A Laser Dosing Study.

All measurements that are completed on paper will be entered by the RA into the database, and a two-step verification system will be used to minimize data entry errors. All records in the database have a form completion status that can be Incomplete (appears as a red circle in the Record Status Panel), Not Verified (yellow circle), or Verified. The RA initially entering the data will save each record entered as Unverified (at which point it will appear as a yellow circle in the Record Status Panel). Then, a second or the same RA at each center will go to each unverified record, compare each entered value to the paper source document, make corrections, and then re-save the record as verified. The unverified and verified identifiers will be unambiguous and easy to evaluate.

4.13 Training

Study-trained doctors who are unaware of treatment randomization will administer diagnostic assessments and rating scales. All raters will be experienced doctors who will have received criteria-specific training in the use of the study measures. Any new evaluators will receive training. Periodically, all study doctors will evaluate an audiotape during a staff meeting. These duplicate evaluations will be used both for calculating kappa coefficients and for monitoring. Differences between raters will be discussed during monitoring to identify reasons for disagreement and improve inter-rater reliability. These procedures will help us ensure that study doctors refine their diagnostic skills and will also establish common guidelines for continued use in diagnostic decision making. Inter-rater agreement will be assessed by evaluating recordings of diagnostic interviews. Kappa coefficients will be calculated every 12 months. If reliability falls below criteria ($ICC \geq 0.8$ for QIDS-C), study doctors will be retrained.

4.14 Compensation

Participants will receive 15.00 soles for each study visit (total expected visits = 20 for those who completed the study, including screening and follow-up visits, maximum total compensation per patient is 300.00 soles).

The sponsor will guarantee transportation, in coordination with the participant and members of the research team, from the research center to the PET scan center and back to the starting point. This applies to participants who are included in the exploratory target research subgroup.

The amount indicated does cover travel and transportation expenses, but should these costs exceed this amount, and in order to protect the rights of the participants, the amount will be reimbursed taking into account the personal and specific considerations of each of these expenses.

Transcranial Near Infrared Laser Therapy in Subjects with Major Depressive Disorder: A Laser Dosing Study.

4.15 Accountability / Investigational Product Control

U.S. federal law and ICH Guideline E6 § 5.14 require that all investigational medical devices be strictly controlled. All investigational devices must be kept in a secure area at clinical sites in compliance with all applicable FDA regulations (U.S. sites).

Principal Investigators or designated study site personnel verifying receipt of devices/device accessories must complete the Device/Accessory Acknowledgement Form and fax a copy to Pthera LLC. Device accountability and acknowledgement records will be maintained at each study site. These records will list all equipment received, date received, serial number of each device. Study site personnel will initiate the log each time the device is used. The use of tPBM-2.0 will also be recorded in the appropriate CRF.

Malfunctioning devices and device accessories, including all components, will be returned to Pthera LLC for investigation at Pthera LLC's expense.

4.16 Publishing

Once the preliminary results for the country and globally are available, they will be communicated to each of the principal investigators.

The principal investigators are responsible for informing each of the subjects enrolled in the study (both those who completed the study and those who were discontinued) of the results of the study. Likewise, the ethics committee and the national health institute (INS) will be informed.

The sponsor agrees to publish the results at the end of the study, whether the results are negative or positive. If authorized by the sponsor, this information may also be published by third parties.

4.17 Clinical Adverse Events

4.17.1 Overview and Definitions

All adverse events will be recorded from the time of Informed Consent until completion or completion of the study. The adverse event CRF must be completed and submitted to the IRB, FDA and Pthera LLC as required. Adverse event management regulations and reporting contained in the FDA and ICH Guidelines will be adhered to.

Consideration of adverse events will hereinafter consist of adverse events, serious adverse events, and adverse device effects, including anticipated and unanticipated adverse device effects.

- **Adverse event** is defined as any unfavorable/undesirable clinical event in a clinical investigation of a subject using a device and/or product that does not necessarily have a causal relationship with this treatment. Therefore, an adverse event can be any unfavorable and/or unintended sign, symptom or disease temporally associated with the use of a product or device, whether or not considered related to it. Only abnormal

Transcranial Near Infrared Laser Therapy in Subjects with Major Depressive Disorder: A Laser Dosing Study.

laboratory values that the investigator considers clinically significant will be classified as adverse events.

- **Serious Adverse Event** is defined as any adverse/undesirable experience that results in any of the following outcomes: 1) death; 2) a life-threatening adverse experience; 3) hospitalization or prolongation of existing hospitalization; 4) a permanent/persistent or significant disability/incapacity, or congenital anomaly/birth defect; 5) major medical events that may not be life-threatening, life-threatening, or require hospitalization may be considered a serious adverse experience when, based on appropriate medical judgment, they may endanger the subject and may require medical or surgical intervention to prevent any of the outcomes listed in this definition.
- **Anticipated adverse device effect** is defined as any adverse effect related to the device or procedure, which is identified in the protocol.
- **Unanticipated adverse device effects** are defined as any serious adverse health or safety effect or any life- or death-threatening problem caused by or associated with a device, if that effect, problem, or death was not previously identified in nature, severity, or degree of occurrence in the research or implementation plan (including a supplemental plan or implementation), or any other serious unanticipated problem associated with a device that relates to the rights, safety, or welfare of subjects.

4.17.2 Safety Monitoring

Study subjects will undergo frequent clinical assessments including depressive scores, concomitant medications, adverse events, and serious adverse events and unexpected device events will be recorded from study entry to completion. In addition, clinicians should monitor the safety of subjects by frequently asking them about their comfort during treatment delivery.

If skin erythema occurs, treatment will be discontinued. Patients will be instructed to contact the principal investigator of the study site or a member of his or her staff at any time between visits regarding adverse events or worsening of symptoms. If at any study visit, the subjects' clinical status significantly worsens from baseline (operationalized as the clinical global impression severity score, CGI-S, of 6 or greater) or if a subject develops active suicidal intent and/or plan, based on the C-SSRS scale and/or the clinical interview, the subject will be referred to the treating doctor to start an antidepressant medication or make appropriate changes in the treatment regimen. If the subject were considered to be in imminent danger as a result of suicidality, he/she would be discontinued from the study and referred to appropriate clinical treatment (see 4.9 Termination).

The two site principal investigators ([name], PI) will have bi-weekly conference calls (which will include all study staff); during these conference calls, they will discuss all adverse event reports to identify any safety concerns, based on such concerns, they may decide to temporarily discontinue study enrollment, modifications to the study protocol or terminate the study.

In addition, a Data and Safety Monitoring Board (DSMB), composed of at least 3 members not directly involved in the study, will review the SAEs annually. The research assistants responsible for data collection and storage will be aware of and comply with all regulatory requirements related to adverse events. In the event that a patient becomes ill or injured as a direct result of study participation, medical care will be provided. All adverse events (and device events) will be tracked to resolution and reported to the MGH or NKI IRB as serious in the event that:

Transcranial Near Infrared Laser Therapy in Subjects with Major Depressive Disorder: A Laser Dosing Study.

1. Not anticipated and possibly study-related (same report as SAE) or
2. If any of the following criteria are encountered: any fatal event, immediately life-threatening event, permanently or substantially disabling event, event requiring or prolonging hospitalization, or any congenital anomaly. This also includes any event that a study investigator judges to impose a significant hazard, contraindication, side effect, or precaution.

An expedited review will be conducted for all events that meet the FDA definition of serious adverse events (SAE), i.e., any fatal event, immediately life-threatening, permanently or substantially disabling event, event requiring or prolonging hospitalization, or any congenital anomaly. This also includes any event that a study investigator or the DSMB judges to impose a significant hazard, contraindication, side effect, or precaution. For the purposes of this study, all SAEs should be reported to the DSMB, regardless of any judgment about their relationship to the study device. All relevant information will be reported to the DSMB for each SAE, including event and outcome information, dosing history of all study TLT applications, concomitant medications, subject medical history and current conditions, and all relevant laboratory data. Per IRB protocol, the principal investigator at each site will report all unanticipated serious adverse events to the IRB within 5 working days / 7 calendar days after the investigator first becomes aware of the problem. If at any time during the course of the study, the DSMB judges that the risk to subjects outweighs the potential benefits, the DSMB will have the discretion and responsibility to recommend that the study be terminated.

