The NIR-TLT delivery is expected to last no longer than 7.15 minutes (429 seconds) in total (simultaneous application to the left and right forehead). The subject will be allowed to rest for 5 minutes after NIR-TLT delivery. The skin at the application sites will be inspected again after laser application. A log will be kept with the dates of delivery of the NIR-TLT.

Near Infrared Transcranial Laser Therapy in Subjects with Major Depressive Disorder: A study of Dosing with Laser.

treatment per study subject. The use of cell phones, tablets, computers or electronic devices will not be allowed during laser administration.

[figure not shown]
During treatment visits and prior to NIR-TLT, study personnel will collect tolerability (safety) and efficacy data:

1. Safety data: SAFTEE-SI (self-assessed), C-SSRS, adverse events and concomitant medication form.
2. Efficacy data - HAMD-17.

In addition to the evaluation described above, during visits 1, 9 and 18:

Prior to the NIR-TLT study, the staff will collect primary efficacy data from metric measurements and brain electrophysiology data:

1. Efficiency data:
 - a. Doctor-administered scales (1): HAMD-17, QIDS-C and CGI-S.
 - b. Patient-Reported Scales (1): ASQ and SDQ
2. Brain Electrophysiology Data - Study personnel will conduct a first 10-minute EEG recording session, treat the patient according to their NIR-TLT group randomization, and then conduct a second 10-minute EEG recording session as soon as possible after the end of treatment, but within 15 minutes.

3. Exploratory PET scan data: A PET scan will be performed on the participants selected to be part of the research subgroup, before the first treatment visit and within 24 hours of the end of the last intervention (visit 18).

4.9.3 Follow-up visit (Post Treatments) - Week 8

Near Infrared Transcranial Laser Therapy in Subjects with Major Depressive Disorder: A study of Dosing with Laser.

The next visit will occur two weeks after the last cerebral blood flow impact visit.

Purpose: The purpose of the follow-up visit is to evaluate the long-term antidepressant effect of NIR-TLT.

Procedures: During the follow-up study, staff will collect tolerability (safety) and efficacy data:

1. Safety data: SAFTEE-SI (self-assessed), adverse events and concomitant medication form.

2. Efficiency data:

- a. Doctor-administered scales (1): HAMD-17, QIDS-C and CGI.
- b. Patient-reported scales (1): SDQ and ASQ.

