4.9.4 Completion

If, during the study, a subject's CGI-S increases more than 2 points or rises above a score of 5, or if they become actively suicidal according to the C-SSRS scale, the subject will be referred to their treating doctor and advised to start or switch to another FDA-approved antidepressant medication. Such subjects may or may not be terminated from the study, depending on the severity of symptoms, at the clinical judgment of the principal investigator. Subjects who are considered actively suicidal and in imminent danger will be terminated from the study and referred to the appropriate local MGH or NKI emergency room for evaluation and subsequent hospitalization, or, if the subject is appropriate for outpatient monitoring, will be referred to their treating doctor for frequent appointments and follow-up. Each subject will have the investigator's contact information, as well as instructions on how to call emergency services, if necessary. We will encourage subjects to continue enrollment in the study through follow-up visits, regardless of discontinuation of NIR-TLT.

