6.4.1 Security Monitoring

Study subjects will undergo frequent clinical assessments including depressive scores, concomitant medications, adverse events, and serious adverse events, and unexpected device events will be recorded from study entry to completion. In addition, clinicians should monitor a subject's safety by frequently asking them about the subject's comfort during treatment delivery.

If skin erythema occurs, treatment will be discontinued. Patients will be instructed to contact the study site principal investigator or a member of his or her staff at any time between visits regarding adverse events or worsening symptoms. If at any study visit, the subjects' clinical status significantly worsens from baseline (operationalized as Clinical Global Impression Severity Score, CGI-S, of 6 or greater) or if a subject becomes actively suicidal with intent and/or plan, as per On the C-SSRS scale and/or clinical interview, the subject will be referred to the treating doctor to start an antidepressant medication or make appropriate changes in the treatment regimen. If the subject were considered to be in imminent danger as a result of suicidality, he/she would be discontinued from the study and referred to appropriate clinical treatment (see Section - 4.9 Termination).

The site will have bi-weekly conference calls with a designated Pthera LLC study monitor (which will include study RA's); During these conference calls, they will discuss all adverse event reports to identify any safety concerns, based on such concerns, they may decide to temporarily discontinue study enrollment, modifications to the study protocol or terminate the study.

In addition, a DSMB, consisting of at least 3 members not directly involved in the study and not employed by Pthera LLC, will review SAE quarterly. Research assistants responsible for data collection and storage will be aware of and comply with all regulatory requirements related to adverse events. In the event that a patient becomes ill or injured as a direct result of study participation, medical care will be provided. All adverse events (and device events) will be tracked to resolution and reported to the DSMB as serious in the event that they were not anticipated and possibly related to the study (same report as SAE) or meet any of the following criteria, any:

- (1) fatal event,
- (2) immediate life-threatening event,
- (3) event of permanent or substantial disability,

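### The Table of Assessments leaves out C-SSRS at visits 10 to 17, against section 4.9.2; secondarily, the CGI-S worsening trigger has two wordings, one of which entrants at 6 or 7 meet without worsening

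*Protocol*

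**What the plan says.** **C-SSRS schedule.** Section 4.9.2 gives two lists. The first, for treatment visits in general, includes "Safety data: SAFTEE-SI (self-assessed), C-SSRS, adverse events and concomitant medication form". The second opens with "In addition to the evaluation described above, during visits 1, 9 and 18" and adds QIDS-C, CGI-S, ASQ, SDQ and EEG; C-SSRS appears only in the first list. The Table of Assessments (section 8) marks C-SSRS at V0, V1, V2 to 8, V9, V18 and V19, and leaves V10 to 17 empty.

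**Use of C-SSRS.** In 4.17.2, active suicidal intent or plan leads to referral, judged "based on the C-SSRS scale and/or the clinical interview". Section 4.9.4 names only the C-SSRS for the same purpose. Section 4.20.1 relies on the visit schedule for early recognition of suicidal ideation.

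**CGI-S trigger.** Section 4.17.2 reads "If at any study visit, the subjects' clinical status significantly worsens from baseline", and adds in parentheses "operationalized as the clinical global impression severity score, CGI-S, of 6 or greater". Section 6.4.1 repeats it: "operationalized as Clinical Global Impression Severity Score, CGI-S, of 6 or greater". Section 4.9.4 acts instead when "a subject's CGI-S increases more than 2 points or rises above a score of 5", and does not say which earlier score the increase is counted from. Inclusion criterion 4 requires CGI-S of at least 4. No criterion sets an upper limit, and section 4.10 gives the range as 1 to 7. CGI-S is scheduled at V0, V1, V9, V18 and V19.

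**The concern.** In a depression trial the suicidality check should not depend on which page of the protocol a site works from. Coordinators commonly work from the schedule table. One who does so here would stop giving C-SSRS after V9 and resume at V18, while a colleague who follows 4.9.2 would continue. Section 4.9.4 makes the C-SSRS the only stated basis for calling a participant actively suicidal, so the gap affects a rule that leads to referral and possibly to termination.

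The CGI-S wording matters less. A rule meant to detect deterioration is written as a level with no baseline term. A participant who is stable at 6, or has improved from 7 to 6, satisfies it as written and would be referred to start or change an antidepressant. Section 4.9.4 points to a rise instead, so the three sections do not give one rule for these participants.

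**Working it through.** The protocol states no figure to reproduce. The check counts visits and enumerates score pairs.

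**1. C-SSRS at treatment visits, from the Table**
- Marked: V1 (1) + V2 to 8 (7) + V9 (1) + V18 (1) = 10 of 18.
- Blank: V10 to 17 = 8 of 18 = 44%.
- Length of the stretch: V9 to V18 is 9 steps at 3 sessions per week, 9 / 3 = 3 weeks.

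**2. Which reading of 4.9.2 fits the Table**
- If the first list in 4.9.2 applied only to visits 1, 9 and 18, the marks at V2 to 8 would have no source in the text.
- If it applies to treatment visits generally, V2 to 8 are explained and V10 to 17 are missing.
- The protocol gives no reason for treating V10 to 17 differently from V2 to 8.

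**3. CGI-S trigger: entry score against later score**

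Rule A (4.17.2 and 6.4.1): later score of 6 or more. Rule B (4.9.4, measured from entry): rise of more than 2, or rise above 5.

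| Entry | Pairs (later 1 to 7) | Rule A met | Rule B met | Disagree |
|---|---|---|---|---|
| 4 | 7 | later 6, 7 | later 6, 7 | 0 |
| 5 | 7 | later 6, 7 | later 6, 7 | 0 |
| 6 | 7 | later 6, 7 | 6 to 6: no, if a rise is needed; 6 to 7: depends on reading | 6 to 6, possibly 6 to 7 |
| 7 | 7 | later 6, 7 | neither, if a rise is needed | 7 to 6, 7 to 7 |

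- Entry at 4 or 5: 0 disagreements in 14 pairs.
- Entry at 6 or 7: Rule A is met in 4 pairs. Three show no rise (6 to 6, 7 to 6, 7 to 7). The fourth, 6 to 7, is a rise that ends above 5, but it does not cross 5, so its status under 4.9.4 depends on how rising above is read.
- From an entry score of 4 or more, the limb of more than 2 points adds nothing: 4 + 3 = 7 is already above 5. It could matter from a lower reference score. For example, 2 to 5 is a rise of 3 but falls short of 6. This is why the missing reference score in 4.9.4 needs filling, all the more because CGI-S is rated at both V0 and V1.

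**4. CGI-S at treatment visits**
- Scheduled at V1, V9 and V18, so 18 - 3 = 15 treatment visits have none.
- V1 to V9 is 8 steps, 8 / 3 = about 2.7 weeks; V9 to V18 is 3 weeks.

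**5. Cost of C-SSRS at V10 to 17**
- 8 per participant; 8 x 112 = 896 at most, if every site had been following the Table.

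**The case against.** *The blank may be a slip.* This is plausible. Seven cells with one empty is a coherent row, but an error in reading the table from the PDF cannot be excluded. If the source table has a mark there, the main point falls away; if it does not, a site would still follow the blank.

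*The first list in 4.9.2 is not a reliable schedule.* It also contains "Efficacy data - HAMD-17", which the Table shows only at V1, V9 and V18 among treatment visits, and which 4.9.2 repeats in its second list. So the list alone does not prove that C-SSRS was meant for each visit. For C-SSRS, however, the Table's own marks at V2 to 8 support the general reading.

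*A reader might infer that suicidality goes unmonitored at V10 to 17.* The protocol does not support that. SAFTEE-SI is scheduled at every treatment visit, and section 4.10 says it covers suicidal thoughts and behaviour. Section 4.17.2 also accepts the clinical interview, and participants are told to report worsening between visits. The gap is in the C-SSRS, not in all monitoring.

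*A reader might infer that the two CGI-S wordings conflict in general.* They agree for every entrant at 4 or 5. The CGI-S figure is also a parenthesis to a sentence about worsening, so a sensible clinician would not record an improved participant as worse. That objection largely stands. What remains is that the text fixes a number, and the number alone gives the wrong answer for some entrants at 6 or 7.

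*A reader might infer that the trigger cannot work at the 15 visits without a scheduled CGI-S.* Nothing bars an unscheduled rating, so the schedule does not disable the rule. The protocol simply does not ask for one.

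*Over-referral is mild, and a strict rise rule could remove protection.* Both stand. The consequence is referral, with termination left to the investigator. A rule that counts only a rise from V1 would drop someone who stays at 6, or who worsened between V0 and V1. The fix has to allow for this.

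**Conclusion.** The C-SSRS discrepancy is the point to correct: the text and the Table give different schedules for 8 of 18 treatment visits, over a stretch of 3 weeks, for a scale that the referral rule names. This assumes that the Table has been read correctly and that the first list in 4.9.2 applies to treatment visits generally.

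The CGI-S wording is a secondary inconsistency, confined to entrants at 6 or 7. Three score pairs meet the absolute rule with no rise, and one more is ambiguous under 4.9.4. These are pairs of scores, not patients. The protocol does not give the share entering at 6 or 7, so no patient count follows.

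The same rules apply in all arms, and nothing here shows between-arm bias. Both corrections are worth making because they cost almost nothing and concern participant safety.

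**What to change.** 1. In the Table of Assessments, mark C-SSRS at V10 to 17 to match 4.9.2. This adds no burden for a site already following 4.9.2. For a site following the Table it adds at most 8 ratings per participant.
2. Use one CGI-S trigger in 4.9.4, 4.17.2 and 6.4.1. It should require an increase from a named baseline score to count as worsening, and state whether that baseline is V0 or V1.
3. For participants who enter at 6 or 7 and stay there, keep referral at the investigator's judgement, so that the new wording does not remove protection.
4. Require an unscheduled CGI-S when worsening is reported or seen at a visit without a scheduled one. Weekly CGI-S is not needed.

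The numeric threshold remains for the sponsor and investigators. The cost is wording in the three trigger sections, an instruction on unscheduled ratings, one Table cell, and a few extra CGI-S ratings. No new instrument is needed.
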